8.1.2 Sample Size Determination

The design incorporates two conditions not usually treated. First, the final group of patients in the phase I component is considered part of the phase II trial. Second, the phase II part has two end-points, toxicity (UT: unacceptable toxicity) and efficacy. The relation between toxicity and efficacy is explicitly taken into account. We test the composite null hypothesis:

$H_0: p(UT) > 0.25 \text{ or } p(PFS > 8 \text{ weeks}) < 0.5 \text{ or } p(PFS > 16 \text{ weeks}) < 0.35$

versus the alternative:

$H_1: p(UT) < 0.05 \text{ and } p(PFS > 8 \text{ weeks}) > 0.66 \text{ and } p(PFS > 16 \text{ weeks}) > 0.56.$

Eleven new patients will be treated in the first stage of the phase 2 component. If 3/17 patients have UTs OR if at most 8/17 are alive and PF at 8 weeks the trial will be either be

suspended for excess toxicity or for futility. The decision for early termination (or amendment) is based on these cut points. If either 3 of 17 stage I patients are DLTs OR if at most 8 of 17 are PF at 8 weeks then terminate or hold up. The final decision point, PFS at 16 weeks is not relevant; the number of such patients does not influence the early decision. The confusion seems to relate to the alternative hypothesis which is couched in terms of 'AND'. It does, of course, require both early and late components of the outcome to be defined. Finally, although 3/17 is less than 0.25, this is the cut point, clearly between 0.05 and 0.25. The early PFS cut point 8/17 is less than 0.5 but is only a cut point.

At that point we will consider protocol amendment. Otherwise, 17 new patients will be recruited. If at least 14/34 patients are PF at 16 weeks AND less than 4/34 have UTs the null hypothesis will be rejected and the treatment declared efficacious. Otherwise it will be declared either too toxic or not efficacious.

Further operating characteristics and statistical details can be found in Appendix 12.3

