12.3 Statistical Considerations and Operating Characteristics for Phase II

Operating characteristics of the design depend on four conditions: toxicity being low (0.05) or high (0.25) and PFS at 16 weeks being low (0.35) or high (0.56). They are summarized below:

1. Toxicity = 0.05 and PFS = 0.56. In this case the power of the study is at least 80%. The chance of early stopping (in error) for excess toxicity is less than 1%. The chance for stopping (in error) for futility varies from 8% to 12% depending on the relation of toxicity to PFS (see details below).
2. Toxicity = 0.05, PFS = 0.35. The chance of early stopping for futility varies from 49% to 57%. The chance of declaring treatment efficacious (type I error) varies from 10% to 21%.
3. Toxicity = 0.25 and PFS = 0.35. Type I error varies from less than 1% to about 5%. Chance of stopping early for either excess toxicity or futility varies from about 26% to about 59%.
4. Toxicity = 0.25 and PFS = 0.56. Type I error varies from about 5% to about 10%. Chance of early stopping for excess toxicity is about 27%.

The term 'UT' here means severe toxicity for which, if frequent enough, dictates dose reduction or trial termination. This early stopping design is an extension of the method of Litwin, Wong and Hudes (Statistics in Medicine, 2007,26:4400-4415). Below, the chance that a patient has a UT and also is PF at 16 weeks is represented by 'a'. 'b', 'c' and 'd', similarly, represent the indicated joint probabilities.

Let $p = p(\text{PFS} > 16 \text{ weeks})$, $p_1 = p(\text{PFS} > 8 \text{ weeks})$ and $p_2 = p(\text{PFS} > 16 \text{ weeks} | \text{PFS} > 8 \text{ weeks})$. Also, let $\text{ptox} = p(\text{UT in 16 weeks})$. Let $\text{ptox1} = f^* \text{ptox} = p(\text{UT in initial 8 week period})$ and $\text{ptox2} = (1-f)^* \text{ptox} = p(\text{UT in 8 through 16 week period} | \text{no UT in the initial 8 weeks})$. Then, $b = p - a$, $c = \text{ptox} - a$ and $d = 1 - a - b - c$. a_1, b_1, c_1 , and d_1 are similarly determined from p_1 and ptox1 . a_2, b_2, c_2 and d_2 are determined likewise, from p_2 and ptox2 .

The table:

$P(\text{UT})$	$1 - p(\text{UT})$	
a	b	$p(\text{PFS} > 16 \text{ weeks}) = 0.56$ (under the alternative hypothesis)
c	d	$p(\text{PFS} < 16 \text{ weeks}) = 0.44$
ptox	$1 - \text{ptox}$	1 ($\text{ptox} = 0.05$ under the alternative hypothesis)

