Illustrates how the joint event probabilities a, b, c and d at the end of the study relate. Namely, if we assign $a = 0.02$ then b, c and d can be determined by subtraction. Here we would get: $b = 0.54$, $c = 0.03$ and $d = 0.41$. For any value of a in $(0, 0.05)$ the other three terms are completely specified. In this design we are considering toxicity to be cumulative. We model the total chance of UT to occur with fraction f in the first interval (0, 8 weeks) and $1-f$ in the final 8 weeks. We have considered fractions $f = 0, 0.25, 0.5, 0.75$ and 1.0 , i.e. $f=0$ implies no toxicity in the first 8 weeks and $f = 1$ implies all toxicity occurs then. The final design is based on $f = \frac{1}{2}$.

P(UT)	1-p(UT)
a1	b1 p(PFS > 8) = 0.66
c1	d1 p(PFS < 8) = 0.34
ptox1	1 - ptox1 1 (ptox1 = ptox2 = 0.025 under the alternative with $f = \frac{1}{2}$) and
P(UT)	1-p(UT)
a2	b2 p(PFS > 16 PFS > 8) = 0.848
c2	d2 p(PFS < 16 PFS > 8) = 0.15
ptox2	1 - ptox2 1

The two tables above characterize the early stopping interval (0, 8 weeks) and final interval (8 weeks, 16 weeks). Numbers in the tables represent the alternative hypothesis. Patients in the initial cohort are represented by the top table (a1, b1, c1, d1) in the initial interval and those who are toxicity and progression free at 8 weeks, hence continue on study are represented by the second table (a2, b2, c2, d2) for their second 8 weeks. Patients recruited into the second cohort, if the study makes it past the first 8 week period, are evaluated only at 16 weeks and are represented by the very first table (a, b, c, d).

The chance of early stopping for excess toxicity, for futility, the chance of final declaration of excess toxicity, the power or type I error were all computed for each of the 4 conditions. Within each of these combinations, the fraction, f, of toxicity born within the first 8 weeks was varied in 5 steps from 0 to 1. We selected the number $f = \frac{1}{2}$ in the belief that toxicity is cumulative and this is the maximum fraction expected to occur in the first half of the trial. Design behavior for $f < \frac{1}{2}$ is ‘better’ than that for $f > \frac{1}{2}$, so is not reported here in detail.

The table below lists the various operating probabilities as functions of ‘a’ for each of the four conditions.

Key:

null = 0: PFS at 16 weeks = 0.35

null = 1: PFS at 16 weeks = 0.56

ntox = 0: Toxicity = 0.05

ntox = 1: Toxicity = 0.25

a: probability that PFS > 16 weeks and patient had UT

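### The operating characteristics in Appendix 12.3 are not those of the decision rule in Section 8.1.2, because the two count progression-free patients and unacceptable toxicities differently

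*Combined protocol and SAP*

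**What the plan says.** Section 8.1.2 sets two looks. At the first, the trial is suspended on this condition: "If 3/17 patients have UTs OR if at most 8/17 are alive and PF at 8 weeks". At the end, "If at least 14/34 patients are PF at 16 weeks AND less than 4/34 have UTs the null hypothesis will be rejected". At both looks UT is a criterion separate from the PF count. The PFS definitions in Sections 8.1.1 and 9 do not list UT as an event.

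Appendix 12.3 gives operating characteristics over a joint probability defined as "a: probability that PFS > 16 weeks and patient had UT", so its model contains patients who are PF and have had a UT. For stage 1 patients in weeks 8 to 16 it says that "those who are toxicity and progression free at 8 weeks, hence continue on study are represented by the second table". For low toxicity and null PFS it reports: "The chance of declaring treatment efficacious (type I error) varies from 10% to 21" percent.

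Two other places bear on the scoring. Section 4.5 withdraws a patient who develops a UT. Section 8.1.1 treats a patient not evaluated at 8 and/or 16 weeks as not alive and progression-free.

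**The concern.** In the appendix tables, type I error halves and futility stopping rises as the joint probability *a* grows. If the PF count ignores UT, as 8.1.2 reads, the overlap between UT and PF should have little effect on either. The pattern suggests that the tables drop patients with a UT from the PF count.

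What is at stake is the go/no-go rule. One PF patient with a UT can decide between 8 and 9 of 17, or between 13 and 14 of 34, and the two sections score that patient differently. A reader of 12.3 is also told that the false-positive risk may be as low as 10%.

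**Working it through.** **Inputs.**
- Null: 16-week PFS 0.35 ("null = 0: PFS at 16 weeks = 0.35") and 8-week PFS 0.50 (Section 8.1.2).
- Alternative: 0.56 and 0.66.
- Low toxicity: "ntox = 0: Toxicity = 0.05". Half of it falls in the first 8 weeks (f = 1/2), so ptox1 = ptox2 = 0.025.
- *a* runs from 0 to 0.05.

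**Cells.** At 16 weeks: a; b = p − a; c = ptox − a; d = 1 − a − b − c. The 8-week cells use p1 with a1 = a/2. The second-interval cells use p2 = p/p1 with a2 = a/2, so p2 = 0.35/0.50 = 0.70 under the null and 0.56/0.66 = 0.848 under the alternative.

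**Enumeration (exact multinomial).** Stage 1 has 17 patients. The first appendix table conditions on at most one UT in the first six. Let S be the success count and U the UT count. Stop if U ≥ 3 or S ≤ 8; otherwise add 17 patients and declare efficacy if S ≥ 14 and U < 4.

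**Reproducing the plan's figures.** Take S as PF and UT-free (cells b1, b2, b). Take final U as second-interval UTs in continuing stage 1 patients plus second-cohort UTs. For a = 0, 0.01, …, 0.05 the type I error is 0.2116, 0.1871, 0.1642, 0.1429, 0.1233, 0.1054, equal to the printed column. Power of 0.8759 to 0.8099 also matches. Without the first-six condition the second table matches too (type I error 0.2106 to 0.1049, power 0.8732 to 0.8072). In the toxicity 0.25 rows that were checked, one cell differs by 0.0001. Both conventions are needed for the match.

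**Changing the conventions one at a time** (UT 5%, first-six condition on, values at a = 0 → a = 0.05):

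| Counting rule | Type I error | Null futility stop | Power | False futility stop |
|---|---|---|---|---|
| Appendix: PF and UT-free; stage 1 week 0-8 UTs omitted at the end | 0.2116 → 0.1054 | 0.4938 → 0.5766 | 0.8759 → 0.8099 | 0.0817 → 0.1213 |
| All PF counted; same UT omission | 0.2116 → 0.2029 | 0.4938 → 0.5003 | 0.8759 → 0.8720 | 0.0817 → 0.0848 |
| 8.1.2 as written: all PF and all UTs counted | 0.2074 → 0.1907 | 0.4938 → 0.5003 | 0.8453 → 0.8382 | 0.0817 → 0.0848 |
| PF and UT-free; all UTs counted | 0.2074 → 0.1037 | 0.4938 → 0.5766 | 0.8453 → 0.7835 | 0.0817 → 0.1213 |

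Without the first-six condition, type I error under the written rule is 0.2063 to 0.1902.

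**Which cause does what.** At a = 0 no patient is both PF and UT, so the PF definition cannot matter there. The gaps at a = 0 (0.2116 against 0.2074; 0.8759 against 0.8453) come wholly from the omitted UTs. The steep fall in type I error comes from the PF count: at a = 0.05 the appendix fixes 16-week PFS at 0.35 but counts only b = 0.35 − 0.05 = 0.30, a harder null than the one in 8.1.2.

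**High toxicity.** At toxicity 0.25 and PFS 0.56 the tables give type I error of 0.1010 (a = 0) to 0.0533 (a = 0.25). The written rule gives 0.0356 to 0.0342. At a = 0 that gap is again wholly due to the UT omission.

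**The case against.** The strongest reply is that the protocol, read as a whole, already scores a patient with a UT as not PF. Section 4.5 withdraws such a patient, 8.1.1 scores an unevaluated patient as not PF, and 8.1.2 refers to 12.3 for details. If no patient with a UT is scanned at 8 or 16 weeks, the two PF counts coincide.

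This shows that the text is open to more than one reading, but it does not rescue the 10% figure. Withdrawal does not imply that there is no scan. Section 4.4 follows progression after active treatment ends, the Schedule of Events provides for off-study imaging, Section 9 asks for progression to be documented after discontinuation, and Table 6-3 allows exceptions to stopping after related grade 4 toxicity. And if patients with a UT were not PF by rule, *a* would be zero by definition and only the row at about 21% would apply.

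A second reply is that the written-rule results for low toxicity all fall within the ranges summarised in 12.3: 19-21% within 10-21%, power above 80%, false futility within 8-12%, null futility within 49-57%. This stands. A reader might infer that the trial carries more false-positive risk than disclosed, or is underpowered. The documents do not support either inference, because the worst case of about 21% is disclosed and does not worsen. Nor is there an arithmetic slip: the appendix is computed correctly for the rule it modelled.

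Section 8.1.1 also calls the analyses estimation only, but 8.1.2 still sets a formal rejection rule to which these error rates are attached.

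**Conclusion.** The mismatch is real and has two parts: which patients count as PF, and which UTs count at the end. At 5% UT the rule as written has type I error of 20.7% to 19.1%, null futility stopping of 49.4% to 50.0%, power of 84.5% to 83.8% and false futility stopping of 8.2% to 8.5%. The 10% low end for type I error and the 57% and 12% upper ends for futility stopping belong to a different rule. Changing the PF count alone gives type I error of 21.2% to 20.3% and power of 87.6% to 87.2%, so it would be wrong to attribute the whole difference to the PF definition.

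The consequence is limited: no cut-off or sample size needs to change.

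The all-PF figures rest on an assumption that the documents do not supply: a stage 1 patient who is PF with a UT at week 8 stays PF to week 16 with the same conditional probability as other patients (0.70 null, 0.848 alternative) and has no second UT.

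**What to change.** 1. State in 8.1.2, for both looks, whether a PF patient with a UT counts as PF. Reconcile this with the withdrawal statement in 4.5 and the unevaluated-patient rule in 8.1.1.
2. Recompute all the 12.3 tables for that rule, counting every UT in the 34 patients, including stage 1 UTs from weeks 0-8, against the limit of fewer than 4.
3. Restate the four summary conditions at the head of 12.3. If all PF patients count, condition 2 becomes about 19-21%.

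Adding a without-UT condition to 8.1.2 and keeping the present tables does not work. With all UTs counted, that rule has power of 84.5% to 78.4%, which is below the stated 80% at a = 0.05.

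The cost is one re-run and a few sentences. If all PF patients count, sample size and cut-offs stay as they are. The price is giving up the 10% low end of the type I error range.

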8.1.3 Randomization and Stratification

No randomization or stratification will be used.

8.1.4 Populations for Analysis

Safety Population: All patients who receive at least one dose of both drugs.

Efficacy Population: All patients who receive at least one dose of both drugs.

8.1.5 Demographic and Baseline Characteristics

Descriptive statistics will be used to summarize baseline characteristics of patients.

8.1.6 Safety Analysis

Safety analysis will be performed by the PI and biostatistics. Safety data will be reviewed by the Extramural Data Safety Monitoring Committee (EDMSC). Each patient will be monitored closely as detailed in the study calendar. Adverse events will be documented and summarized in table form. Interim analysis of toxicity, outcome and ongoing scientific investigations may be performed every 3 months by the Extramural Data Safety Monitoring Committee (EDSMC). In this capacity the EDSMC will serve as an advisory committee to ERP and FCCC IRB. The EDSMC will review those aspects of this trial that are outlined in the responsibilities section of the ERP Data and Safety Monitoring Plan (DSMP). If the committee decides that changes should be made to this trial, it will make recommendations in writing to the Extramural Research Committee and Division Medical Director and PI which, in turn, have the authority to approve or disapprove these recommendations. These changes will be discussed with the Study Principal Investigator before they are

implemented. These changes may include early termination of accrual. Other changes might include altering the accrual goals or changing the eligibility criteria for the trial.

9 MEASUREMENT OF EFFECT

Response and progression will be evaluated in this study using the international criteria proposed by the revised Response Evaluation Criteria in Solid Tumors (RECIST) guideline (version 1.1).⁵³ Changes in the largest diameter (unidimensional measurement) of the tumor lesions and the shortest diameter in the case of malignant lymph nodes are used in the RECIST criteria.

All patients will be evaluable for toxicity from the time of their first treatment with pegylated interferon and ixazomib. Only those patients with evaluable and measurable disease will be enrolled and thus evaluable for objective response. A patient must have had at least one cycle of therapy (28 days) and have their disease re-evaluated to be considered evaluable for response and PFS.

Measurable Disease: Measurable lesions are defined as those that can be accurately measured in at least one dimension (longest diameter for non-nodal lesions and short axis for nodal lesions to be recorded) as > 20 mm by chest x-ray, as > 10 mm with CT scan, or > 10 mm with calipers by clinical exam. All tumor measurements must be recorded in millimeters (or decimal fractions of centimeters).

Malignant lymph nodes: To be considered pathologically enlarged and measurable, a lymph node must be > 15 mm in short axis when assessed by CT scan (CT scan slice thickness recommended to be no greater than 5 mm). At baseline and in follow-up, only the short axis will be measured and followed.

Non-measurable disease: All other lesions (or sites of disease), including small lesions (longest diameter < 10 mm or pathological lymph nodes with > 10 to < 15 mm short axis) are considered non-measurable disease. Bone lesions, leptomeningeal disease, ascites, pleural/pericardial effusions, lymphangitis cutis/pulmonitis, inflammatory breast disease, and abdominal masses (not followed by CT or MRI) are considered as non-measurable.

Note: Cystic lesions that meet the criteria for radiographically defined simple cysts should not be considered as malignant lesions (neither measurable nor non-measurable) since they are, by definition, simple cysts.

‘Cystic lesions’ thought to represent cystic metastases can be considered as measurable lesions if they meet the definition of measurability described above. However, if non-cystic lesions are present in the same patient, these are preferred for selection as target lesions.

Target lesions: All measurable lesions up to a maximum of 2 lesions per organ and 5 lesions in total, representative of all involved organs, should be identified as **target lesions** and recorded and measured at baseline. Target lesions should be selected on the basis of their size (lesions with the longest diameter), be representative of all involved organs, but in

addition should be those that lend themselves to reproducible repeated measurements. It may be the case that, on occasion, the largest lesion does not lend itself to reproducible measurement in which circumstance, the next largest lesion which can be measured reproducible should be selected. A sum of the diameters (longest for non-nodal lesions, short axis for nodal lesions) for all target lesions will be calculated and reported as the baseline sum diameters. If lymph nodes are to be included in the sum, then only the short axis is added into the sum. The baseline sum diameters will be used as reference to further characterize any objective tumor regression in the measurable dimension of the disease.

Non-target lesions All other lesions (or sites of disease) including any measurable lesions over and above the 5 target lesions should be identified as **non-target lesions** and should also be recorded at baseline. Measurements of these lesions are not required, but the presence, absence, or in rare cases unequivocal progression of each should be noted throughout follow-up.

All measurements should be taken and recorded in metric notation using a ruler or calipers.

The same method of assessment and the same technique should be used to characterize each identified and reported lesion at baseline and during follow-up. Imaging-based evaluation is preferred to evaluation by clinical examination unless the lesion(s) being followed cannot be imaged, but are assessable by clinical exam.

Clinical lesions: Clinical lesions will only be considered measurable when they are superficial (e.g., skin nodules and palpable lymph nodes) and > 10 mm diameter as assessed using calipers (e.g., skin nodules). In the case of skin lesions, documentation by color photography including a ruler to estimate the size of the lesion is recommended.

Conventional CT and MRI This guideline has defined measurability of lesions on CT scan based on the assumption that CT slice thickness is 5 mm or less. If CT scans have slice thickness greater than 5 mm, the minimum size for a measurable lesion should be twice the slice thickness. MRI is also acceptable in certain situations (e.g., for body scans).

Use of MRI remains a complex issue. MRI has excellent contrast, spatial, and temporal resolution; however, there are many image acquisition variables involved in MRI which greatly impact image quality, lesion conspicuity, and measurement. Furthermore, the availability of MRI is variable globally. As with CT, if an MRI is performed, the technical specifications of the scanning sequences used should be optimized for the evaluation of the type and site of disease. Furthermore, as with CT, the modality used at follow-up should be the same as was used at baseline and the lesions should be measured/assessed on the same pulse sequence. It is beyond the scope of the RECIST guidelines to prescribe specific MRI pulse sequence parameters for all scanners, body parts, and diseases. Ideally, the same type of scanner should be used and the image acquisition protocol should be followed as closely as possible to prior scans. Body scans should be performed with breath-holding techniques, if possible.

PET-CT should not be used as an imaging modality

Ultrasound: Ultrasound is not useful in assessment of lesion size and should not be used as a method of measurement.

Cytology, Histology: These techniques can be used to differentiate between partial responses (PR) and complete responses (CR) in rare cases (e.g., residual lesions in tumor types, such as germ cell tumors where known residual benign tumors can remain).

The cytological confirmation of the neoplastic origin of any effusion that appears or worsens during treatment when the measurable tumor has met criteria for response or stable disease is mandatory to differentiate between response or stable disease (an effusion may be a side effect of the treatment) and progressive disease.

Evaluation of Target Lesions

Response	Evaluation of Target Lesions
Complete Response (CR)	Disappearance of all target lesions. Any pathological lymph nodes (whether target or non-target) must have reduction in short axis to < 10 mm.
Partial Response (PR)	At least a 30% decrease in the sum of diameters of target lesions, taking as reference the baseline sum of diameters.
Progressive Disease (PD)	
At least a 20% increase in the sum of diameters of target lesions, taking as reference the smallest sum on study (this includes the baseline sum if that is the smallest on study). In addition to the relative increase of 20%, the sum must also demonstrate an absolute increase of at least 5 mm.
 
Note: the appearance of one or more new lesions is also considered progression.

Stable Disease (SD)	Neither sufficient shrinkage to qualify for PR nor sufficient increase to qualify for PD, taking as reference the smallest sum diameters while on study.

Evaluation of Non-Target Lesions

Response	Evaluation of Target Lesions
Complete Response (CR)	Disappearance of all non-target lesions and normalization of tumor marker level. All lymph nodes must be non-pathological in size (< 10 mm short axis).
Non-CR/ Non-PD [Incomplete response/ Stable Disease (SD)]	Persistence of one or more non-target lesion(s) and/or maintenance of tumor marker level above the normal limits.
Progressive Disease (PD)	
Appearance of one or more new lesions and/or unequivocal progression of existing non-target lesions. Unequivocal progression should not normally trump target lesion status. It must be representative of overall disease status change, not a single lesion increase.
 
Although a clear progression of 'non-target' lesions only is exceptional, the opinion of the treating physician should prevail in such circumstances, and the progression status should be confirmed at a later time by the review panel (or Principal Investigator).

Evaluation of Best Overall Response

The best overall response is the best response recorded from the start of the treatment until disease progression/recurrence (taking as reference for progressive disease the smallest measurements recorded since the treatment started).

Target lesions	Non-Target Lesions	New Lesions	Overall Response	Best Overall Response when Confirmation is Required*
CR	CR	No	CR	≥ 4 wks. Confirmation **
CR	Non-CR/Non-PD	No	PR	≥ 4 wks. Confirmation **
CR	Not evaluated	No	PR	
PR	Non-CR/Non-PD/not evaluated	No	PR	
SD	Non-CR/Non-PD/not evaluated	No	SD	Documented at least once ≥ 4 wks from baseline **
PD	Any	Yes or No	PD	
Any	PD ***	Yes or No	PD	
Any	Any	Yes	PD	No prior SD, PR or CR

* See RECIST 1 manuscript for further details on what is evidence of a new lesion.
 ** Only for non-randomized trials with response as primary endpoint.
 *** In exceptional circumstances, unequivocal progression in non-target lesions may be accepted as disease progression.

Note: Patients with a global deterioration of health status requiring discontinuation of treatment without objective evidence of disease progression at that time should be reported as “*symptomatic deterioration*.” Every effort should be made to document the objective progression even after discontinuation of treatment.

Progression-Free Survival

PFS is defined as the duration of time from start of treatment to time of progression or death, whichever occurs first.

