4.3 Number of Patients

For the phase I portion of the study we will enroll at a minimum 12 and at a maximum 18 (please see Section 4.1 and 7 for more on the statistical design). For the phase II portion of the study we will enroll up to 31 patients. For phase II portion, a patient is considered enrolled at cycle 1 day 1 when at least one of the drugs has been administered. All patients will be included in the toxicity and PFS and RR analysis.

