8.1.1 Definition of Phase II and exploratory endpoints and Analytic Plan

The phase II dose will be determined by an initial standard '3+3' phase I component as described in Section 4.1. Once a RP2D is reached, the phase II will begin.

Definition of phase II primary endpoint: Progression free survival at 8 and 16 weeks using RECIST v 1.1, defined from date of treatment initiation to date of progression according to RECIST or death, or is censored at the date of the last imaging. If patient is not evaluated at 8 and/or 16 weeks then the patient is not considered as alive and progression-free.

Definition of secondary outcomes/endpoints:

1. Composite of unacceptable toxicity at 8 weeks (grade 4 non-hematologic toxicity thought to be definitely, probably or possibly related to study drug)
2. Overall response using RECIST v1.1.

Definition of exploratory objectives:

1. Changes in STAT1 phosphorylation and MHC1 up regulation in PBMCs from baseline to week 2, 3, 7, EOT.
2. Degree of desmoplasia in archived FFPE tumor samples and change in serum IL-6
3. Degree of nuclear NF- κ B p65 and STAT1 in archived FFPE tumor samples

Analytic plan for primary and secondary objectives:

Kaplan Meier curves will be used to estimate the distribution of progression free survival, median survival, and 1-year survival. Proportions, 95% confidence intervals, will be used to characterize composite rate of unacceptable toxicity and overall response rate. All analyses are for estimation only, and no larger inference will be generated given the sample size of the study.

Analytic plan for exploratory objectives:

Pre- and post- treatment phosphorylation changes in pSTAT1 and MHC1 (flow data, the MFIs will be log10) and serum IL-6 will be analyzed by paired t-tests. Degree of desmoplasia and nuclear NF- κ B and STAT1 will be quantified using standard immunohistochemical methods. Statistical analysis for western blots and responders vs non-responders tumor immunohistochemistry will be performed using non-parametric Mann-Whitney test and/or paired t-tests.

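### Four sections define the analysed patients differently, and Appendix 12.3 omits some unacceptable toxicities from the final count; with all of them counted, power can fall below the stated 80%.

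*Combined protocol and SAP*

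**What the plan says.** **Section 4.3.** In phase II "a patient is considered enrolled at cycle 1 day 1 when at least one of the drugs has been administered", and "All patients will be included in the toxicity and PFS and RR analysis".

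**Section 8.1.1.** The primary endpoint definition contains two rules for incomplete follow-up. PFS "is censored at the date of the last imaging", and "If patient is not evaluated at 8 and/or 16 weeks then the patient is not considered as alive and progression-free".

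**Section 8.1.4.** The first definition reads "Safety Population: All patients who receive at least one dose of both drugs". The second sets the same condition: "Efficacy Population: All patients who receive at least one dose of both drugs". Under 4.2, pIFN is given every week, while ixazomib is given in weeks 2 to 4 of each cycle.

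**Section 9.** The efficacy condition is strict: "must have had at least one cycle of therapy (28 days) and have their disease re-evaluated to be considered evaluable for response and PFS". On safety: "All patients will be evaluable for toxicity from the time of their first treatment with pegylated interferon and ixazomib".

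**Section 8.1.2.** The trial is suspended if 3 of 17 have UT or at most 8 of 17 are progression-free at 8 weeks. It succeeds if at least 14 of 34 are progression-free at 16 weeks and fewer than 4 of 34 have UT.

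**Appendix 12.3.** It treats toxicity as cumulative and puts power at 80% or more.

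**Phase I.** Section 4.1 counts only patients who took ixazomib and replaces those who stop in the first 28 days for reasons other than a DLT. The DLT window in 4.1.1 is the first 28 days on study. Section 6.13 says withdrawn patients are not replaced.

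**The concern.** The PFS proportion, the response rate and the UT count could each be computed on different patients, and nothing says which rule prevails. The excluded patients are not a random subset. The re-evaluation condition in section 9 removes patients who die or leave before a scan, all of whom are failures under 8.1.1. The both-drugs condition in 8.1.4 removes a patient with UT on pIFN alone in week 1, because 4.5 withdraws such a patient before ixazomib starts. The cuts in 8.1.2 are counts out of exactly 17 and 34, with no rule for smaller denominators, so one patient can change a decision.

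Appendix 12.3 raises the same question for toxicity: whether its error rates were computed for the UT count that 8.1.2 prescribes.

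**Working it through.** **1. The same patient under each rule**

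| Patient | 4.3 with 8.1.1 | 8.1.4 | Section 9 |
|---|---|---|---|
| Stops after week 1, pIFN only, never scanned | counted, failure | in neither population | not evaluable for PFS or response |
| Both drugs, dies before day 28 | counted, PFS event | in both | not evaluable for PFS or response |
| Both drugs for 28 days, no re-evaluation | counted, failure | in both | not evaluable for PFS or response |
| Stops before day 28, later scanned progression-free at 16 weeks | counted, success | in only if ixazomib was taken | not evaluable for PFS or response |
| UT in week 1 on pIFN alone | counted as UT | outside the safety population | unclear: the wording names both drugs |

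**2. Effect on proportions and cuts**

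- Three unassessed failures dropped: 13/34 = 38.2% becomes 13/31 = 41.9%. For comparison, 14/34 = 41.2%. The count stays at 13.
- One early stopper scanned progression-free dropped: 14/34 (efficacious) becomes 13/33 = 39.4%.
- One UT dropped: 3/17 (suspend) becomes 2/16, or 4/34 (too toxic) becomes 3/33.

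**3. Reproducing Appendix 12.3**

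Inputs from 8.1.2 and 12.3: 6 + 11 + 17 patients; 8- and 16-week PFS of 0.66 and 0.56 (alternative) or 0.50 and 0.35 (null); UT of 0.05 or 0.25, half of it in the first 8 weeks (f = 1/2); *a* = probability of UT together with being progression-free at 16 weeks. I split *a* between the two intervals in the same proportion f and counted a patient as progression-free only if also free of UT.

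Early toxicity stop, second table: P(Bin(17, 0.025) ≥ 3) = 0.0082 and P(Bin(17, 0.125) ≥ 3) = 0.3591. Conditioning on at most one UT in the first six gives 0.0059 and 0.2690, as in the first table. Futility stopping in the first table also matches at *a* = 0 (0.4938 null, 0.0817 alternative).

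For the final stage (success if progression-free ≥ 14/34 and UT ≤ 3/34) I enumerated three ways of counting UT exactly:

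- A: all UTs among the 34;
- B: first-8-week UTs in the initial 17, plus UTs in the second cohort;
- C: UTs in weeks 8 to 16 in the initial 17, plus UTs in the second cohort.

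| First table | Printed | C | B | A |
|---|---|---|---|---|
| Power, *a* = 0 | 0.8759 | 0.8759 | 0.8720 | 0.8453 |
| Power, *a* = 0.05 | 0.8099 | 0.8099 | 0.8061 | 0.7835 |
| Alpha, UT 0.05, PFS 0.35, *a* = 0 | 0.2116 | 0.2116 | 0.2106 | 0.2074 |
| Alpha, UT 0.05, PFS 0.35, *a* = 0.05 | 0.1054 | 0.1054 | 0.1049 | 0.1037 |
| Alpha, UT 0.25, PFS 0.56, *a* = 0 | 0.1010 | 0.1010 | 0.1058 | 0.0356 |
| Alpha, UT 0.25, PFS 0.56, *a* = 0.25 | 0.0533 | 0.0533 | 0.0479 | 0.0224 |

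Only C matches. It also matches the printed probability of a final too-toxic decision (0.0115 null and 0.0234 alternative, at UT 0.05 and *a* = 0) and the second table (power 0.8732 and 0.8072). C omits exactly the UTs seen before the interim look.

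Under A, power for *a* = 0, 0.01, …, 0.05 is 0.845, 0.836, 0.824, 0.812, 0.799 and 0.784 (first table). In the second table it is 0.8415 at *a* = 0 and 0.7798 at *a* = 0.05.

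**4. Scenarios on assumed shares**

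- *Week-1 UT.* The documents give no share, and it may be near zero. If 5% of 8-week UTs fall in week 1 and drop out, the rate becomes 0.125 × 0.95 = 0.11875. At p(UT) = 0.25 the early toxicity stop then falls from 0.359 to 0.328, or from 0.269 to 0.245 under the first-six restriction.
- *Unassessed patients scored as failures.* If 0.66 and 0.56 describe assessed patients only, both are multiplied by 1 − u. First-table power, from *a* = 0 to 0.05: with u = 5%, 0.81 to 0.72 under C and 0.79 to 0.70 under A; with u = 10%, 0.73 to 0.61 under C and 0.71 to 0.60 under A.

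**The case against.** Most of the text points one way. Section 8.1.2 speaks of patients treated and recruited, 4.3 includes everyone, and the missing-assessment rule sits inside the primary endpoint definition. The section 9 sentence may only label patients within a passage on RECIST. Because the cuts are counts, 13/31 still has only 13 successes and does not meet a cut of 14. The 14/34 to 13/33 case is rare: it needs a very early stopper with a progression-free scan at week 16. An off-study scan taken at stopping cannot supply that, and the follow-up for progression in 4.4 has no scan dates. Censoring reads naturally as belonging to the Kaplan-Meier curve. The power shortfall arises only at *a* = 0.04 and 0.05, when at least four fifths of UT patients are also progression-free at 16 weeks, and is at most 2.0 points. Counting all UTs lowers the type I error.

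These points limit the size, and I accept them on size. They do not remove the conflict. Section 8.1.4 is an explicit population definition that contradicts 4.3 for both safety and efficacy. The UT cuts can change on one excluded patient. The dropped failures would still inflate the reported rates. The appendix figures do not describe the rule written in 8.1.2.

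**Conclusion.** The concern holds and should be fixed. The contradiction between 4.3, 8.1.1, 8.1.4 and 9 is textual and needs no assumption. Its most plausible effect on a decision is a week-1 UT on pIFN alone falling outside the safety set; how often that happens is unknown. For PFS the usual effect is an inflated reported proportion rather than a changed count.

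The finding on Appendix 12.3 is exact for the design parameters and f = 1/2. Under the UT rule as written, first-table power is 0.845 to 0.784, so 80% or more is not supported at *a* = 0.04 and above. At UT 0.25 and PFS 0.56, type I error is 0.036 at *a* = 0 and 0.022 at *a* = 0.25, against the printed 0.101 and 0.053.

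Two smaller points also stand. Section 8.1.1 does not assign censoring and failure scoring to separate analyses. In phase I, 4.1 counts only patients who took ixazomib, yet its replacement sentence implies that DLT stops are kept, so a week-1 DLT before ixazomib is handled inconsistently.

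**What to change.** - **8.1.4 and 8.1.2:** define the phase II safety and efficacy populations as all patients given at least one dose of either drug, as in 4.3, and state that this set supplies the 17 and the 34.
- **Section 9:** delete the evaluability condition for PFS and response, or keep it for a labelled sensitivity analysis only. Score treated but unassessed patients as not progression-free at 8 and 16 weeks and as non-responders. Start toxicity evaluability at the first dose of either drug.
- **8.1.1:** apply failure scoring to the 8- and 16-week proportions and the cuts, and censoring at last imaging only to the Kaplan-Meier curve.
- **Appendix 12.3:** rerun the tables with every UT among the 34 in the final count, and restate the power.
- **Phase I:** reconcile 4.1 with the DLT window in 4.1.1, and reconcile the replacement statements in 4.1 and 6.13 for the six patients shared by both phases.

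The cost is wording in 4.1, 6.13, 8.1.1, 8.1.2, 8.1.4 and 9, and one rerun. Reported PFS and response rates may be lower. The sponsor should also say whether 0.66 and 0.56 already allow for unassessed patients; if not, power falls as shown in step 4 of the working.
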